11.2.1.1. In-Clinic Assessments (CVT-301 Treatment Group)

See [Section 11.1.12.1](#).

11.2.1.2. At-Home Assessments

11.2.1.2.1. PD Diary

During the 3 consecutive days prior to SV2 and TV/OV1, TV/OV2, TV/OV3, TV/OV4, TV/OV5, and TV/OV6, patients in the CVT-301 treatment group will record their waking ON/OFF status (time OFF, time ON without dyskinesia, time ON with non-troublesome dyskinesia, time ON with troublesome dyskinesia) and time asleep in the PD Diary (also referred to as the PD Home Diary or “Hauser diary”) ([Hauser 2000](#)).

Patients in the observational cohort will complete the PD Diary for 3 consecutive days prior to SV2 and TV/OV1, but will not be required to complete the PD Diary for the remainder of the study.

New diaries will be distributed to appropriate patients at each study visit, except for TV/OV6, and patients will bring the completed diaries to the following clinic visit. Information in the diaries will be reviewed, signed, and dated by clinic staff.

11.2.1.2.2. Screening ON/OFF Episodes Log (for the Screening Period)

All patients will record the discrete number of OFF episodes experienced by the patient during their waking day in the Screening ON/OFF Episodes Log for the 3 consecutive days prior to SV2 and TV/OV1. These logs will be distributed at SV1 and SV2, and patients will bring the completed logs to the clinic at SV2 and TV/OV1. Information in the logs will be reviewed, signed, and dated by clinic staff.

11.2.1.2.3. Inhaled Dosing Log (for the Treatment Period) for CVT-301 Treatment Group

Every day during the treatment period, patients in the CVT-301 treatment group will record the number of times the inhaler was used and the number of capsules used for each inhalation treatment. New logs will be distributed at TV/OV1, TV/OV2, TV/OV3, TV/OV4, and TV/OV5, and patients will bring the completed logs to the clinic at TV/OV2, TV/OV3, TV/OV4, TV/OV5, and TV/OV6. Information in the logs will be reviewed and recorded by clinic staff.

11.2.2. UPDRS Part 3 (CVT-301 Treatment Group)

The UPDRS Part 3 is the motor section of the UPDRS examination, given by interview with actions by the patient. Some questions require multiple ratings to be assigned to each extremity. The areas addressed by this exam include speech, facial expression, tremor at rest, postural tremor, rigidity, finger taps, hand movements, rapid alternating movement (hands), leg agility, arising from a chair, posture, gait, postural stability, and body bradykinesia/ hypokinesia.

The UPDRS Part 3 will be assessed at screening in both ON and OFF states to familiarize the patient with the study evaluations as well as to document each patient’s response to his/her own PD medications; to enter the study, the difference between UPDRS Part 3 scores in the ON and OFF states must be $\geq 25\%$.

The percent difference is calculated as follows:

$$([\text{UPDRS III value in OFF state}] - [\text{UPDRS III value in ON state}]) / \text{UPDRS III value in OFF state}$$

The UPDRS Part 3 assessments will be done for the CVT-301 patients at TV/OV2, TV/OV3, TV/OV4, TV/OV5 and TV/OV6, immediately before and at various time points after study medication dosing, as indicated in the time and events tables in [Appendix 2](#) through [Appendix 15](#).

11.2.3. PDQ-39

The PDQ-39 is a self-report questionnaire that covers 8 aspects of quality of life: mobility, activities of daily living, emotions, stigma, social support, cognitions, communication, and bodily discomfort. Scores are reported for each of the 8 quality of life scales and for the total of all 39 items.

The PDQ-39 will be completed upon arrival for patients assigned to the CVT-301 treatment group and the observational cohort as indicated in the time and events tables in [Appendix 2](#) through [Appendix 15](#).

11.2.4. PGI-C (CVT-301 Treatment Group)

For this study, the PGI-C is a 7-point scale that requires the patient to rate their overall condition with regard to PD by answering the following question: **How has the addition of study drug changed your Parkinson's disease?** This change is rated as 1 = much improved; 2 = improved; 3 = a little improved; 4 = no change; 5 = a little worse; 6 = worse; or 7 = much worse. If the assessment is not done, then the score is marked as 0; any values of zero are not included in any analyses and thus are treated as missing.

The PGI-C scale will be completed by the patients in the CVT-301 treatment group as indicated in the time and events tables in [Appendix 2](#) through [Appendix 15](#).

11.2.5. Schwab & England Activities of Daily Living

The S&E ADL scale will be completed by a qualified rater upon arrival for patients assigned to the CVT-301 treatment group and the observational cohort as indicated in the time and events tables in [Appendix 2](#) through [Appendix 15](#), preferably while the patient is in the ON state.

11.2.6. UPDRS Part 2

The UPDRS Part 2 is an evaluation of the ADL; this will be completed by a qualified rater upon arrival for patients assigned to the CVT-301 treatment group and the observational cohort as indicated in the time and events tables in [Appendix 2](#) through [Appendix 15](#), preferably while the patient is in the ON state.

11.3. Other Assessments Used for Baseline Disease Characteristics for all Patients

Patients' PD diagnosis will be documented by the UK Brain Bank criteria, and PD severity will be staged using the modified Hoehn and Yahr disease severity scale. The MMSE is used to assess the patient's cognitive state.

11.3.1. UK Brain Bank Criteria

Steps 1 and 2 of the UK Brain Bank criteria will be used to confirm the patient's PD diagnosis. Step 1 requires that the patient have certain signs and symptoms of Parkinsonian syndrome, and Step 2 lists exclusion criteria that the patient must not have to be diagnosed with PD. The UK Brain Bank criteria are presented in [Appendix 18](#) and discussed in [Hughes \(1992\)](#).

11.3.2. Modified Hoehn and Yahr PD Severity Scale Assessment

PD severity will be staged using the modified Hoehn and Yahr disease severity scale (refer to [Appendix 19](#)).

11.3.3. MMSE

The MMSE is a brief, 30-point test used to screen for cognitive impairment. The categories tested include orientation to time, orientation to place, registration, attention and calculation, recall, language, repetition, and complex commands. Any score ≥ 25 points is considered normal. Scores below 25 can indicate mild (21-24 points), moderate (10-20), or severe (0-9) cognitive impairment.

11.3.4. Pulmonary Function Baseline Questionnaire

The patient's pulmonary history will be recorded by completing the Pulmonary Function Baseline Questionnaire at screening. Site staff will administer the Pulmonary Function Baseline Questionnaire to all patients. The questionnaire includes sections for recording asthma, COPD, and other lung or airway disease symptom history. There is also a section for recording patient-reported instances of current pulmonary symptomology.

11.4. Appropriateness of Measurements

All safety assessments to be used in this study are commonly used, standard measurements frequently seen in PD studies and/or pulmonary studies. The modified Hoehn and Yahr disease severity scale is a validated method of assessing the severity of PD, and the UPDRS Part 3 is a validated tool measuring the motor aspects of a PD patient. The UPDRS Part 2, UPDRS Part 4, and S&E ADL rating scales are also standard tools for the assessment of PD patients. Rater training in UPDRS Part 2, UPDRS Part 3, UPDRS Part 4, S&E ADL and C-SSRS scales will be given to clinic staff members who plan to administer the tests. The PDQ-39 is a validated quality of life measure for PD patients. The PGI-C scale is a tool for assessing patient-perceived changes in their overall disease condition. The PD Diary to be used in this study (also referred to as the Hauser diary) has been validated for use in PD patients as a tool to assess patient-defined clinical status at home over a period of time (recording daily OFF time, ON time, and time with non-troublesome and troublesome dyskinesia).

12. DATA MANAGEMENT AND STATISTICAL ANALYSIS

Completed eCRFs for this study will be entered by electronic data capture (EDC) into the study database. The statistical analysis of these data will be performed by the Sponsor or its representative. The statistical evaluation will be performed using the Statistical Analysis Software (SAS[®]) Version 9.3 or higher (SAS Institute, Cary, NC). All data will be listed, and

summary tables will be provided. Summary statistics will be presented by treatment group (when applicable).

This section describes the statistical analysis as it is foreseen at the time of planning the study. Any major deviations from this plan, the reasons for such deviations, and all alternative or additional statistical analyses that may be performed will be described in the statistical analysis plan (SAP), which will give a detailed technical description of all statistical analyses. The SAP will serve as a compliment to the protocol and supersedes it in case of differences.

12.1. Determination of Sample Size

Approximately 250 CVT-301 treatment patients and 115 control patients will be enrolled in this study. It is assumed that the drop-out rate will be approximately 25%.

Assuming that there is no difference in the changes from baseline between the CVT-301-treated patients and the observational cohort in regards to FEV1, the study has the following power for the comparison between the 2 groups. The upper limit of the 95% confidence interval for the difference between the 2 groups in change from baseline in FEV1 will be less than 0.121 L with 90% power, assuming 188 and 86 patients completing the study in the CVT-301 treatment group and observational cohort, respectively.

12.2. Study Populations

All patients who are enrolled in CVT-301-005 and receive at least 1 dose of CVT-301 will be included in the safety population. The patients in the observational cohort will be included in the analyses if they provide any data after TV/OV1.

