CVT-301-treated patients will be followed in the clinic for the following efficacy measures: serial assessments of UPDRS Part 3 motor score following treatment in the clinic, the occurrence and severity of dyskinesia following treatment in the clinic, the occurrence of ON states during the post-treatment period, the 39-Item Parkinson's Disease Questionnaire (PDQ-39), the Patient Global Impression of Change (PGI-C) rating scale, the Schwab and England (S&E) Activities of Daily Living (ADL) score; UPDRS Part 2 score, and UPDRS Part 4 (Questions 32-35 and 36-39) score. In addition, the total daily ON time without dyskinesia, total daily ON time with troublesome dyskinesia, total daily ON time with non-troublesome dyskinesia, and total daily OFF time will be evaluated in the CVT-301-treated patients based on the PD Diary, which will be completed for the 3 consecutive days prior to SV2, TV/OV1, TV/OV2, TV/OV3, TV/OV4, TV/OV5, and TV/OV6.

All patients, regardless of treatment assignment, will undergo the safety assessments. Patient safety will be evaluated using adverse event (AE) reports, physical examination, vital signs (blood pressure [BP], heart rate [HR], and respiratory rate [RR]), clinical laboratory tests, 12-lead electrocardiograms (ECGs), spirometry, carbon monoxide diffusing capacity (DLco) maneuver, the Parkinson's Disease Impulsive-Compulsive Disorders Questionnaire (QUIP), the Epworth Sleepiness Scale, and the Columbia-Suicide Severity Rating Scale (C-SSRS).

The use of a randomized observational cohort in this study is to permit long-term contemporaneous temporal comparison to CVT-301-treated patients to describe any potential effects of CVT-301 with respect to lung function measurements. These control patients, who are eligible to use any approved treatments to manage their PD motor symptoms, represent a randomized study population that remains naïve to inhalation treatment (to avoid potential confounding interpretation of lung function data) for their PD which is required to ascertain the underlying variability in spirometry and DLco endpoints. Only a limited number of efficacy assessments will be evaluated in the patients randomized to the observational cohort. Selected efficacy measures to assess effects of CVT-301 will be evaluated in the open-label CVT-301-treated patients who use CVT-301 inhalation as a treatment of OFF symptoms.

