6. STUDY OBJECTIVES

Primary Objective

- To characterize the pulmonary safety, as assessed by spirometry (forced expiratory volume in 1 second [FEV1], forced vital capacity [FVC], and FEV1/ FVC ratio), over a 12-month period within the CVT-301-treated patients.

Secondary Objectives

- To characterize the pulmonary safety, as assessed by spirometry (FEV1, FVC, and FEV1/FVC ratio), over a 12-month period in the observational ('standard of care') cohort.
- To estimate the difference between the CVT-301-patients and the observational cohort on measures of pulmonary safety.
- To characterize the effects of CVT-301 on safety over a 12-month period: safety will be assessed by AE reports, physical examination, standard and orthostatic vital signs (BP, HR, and RR), clinical laboratory tests, 12-lead ECGs, QUIP, the Epworth Sleepiness Scale, and the C-SSRS.
- To evaluate the effect of CVT-301 on mean change from baseline in the UPDRS Part 4 measures of motor fluctuations (dyskinesias [Q32-35] and wearing off [Q36-39]) measured pre-dose at 6 and 12 months after the initiation of CVT-301 treatment.
- To characterize the occurrence and severity of examiner-rated dyskinesia following treatment of patients experiencing an OFF episode in the clinic over a 12-month period.
- To describe the effects of CVT-301 on DLco over a 12-month period.

Exploratory Efficacy Objectives

- Change from pre-dose in UPDRS Part 3 motor score at 10, 20, 30, and 60 minutes following treatment of patients experiencing an OFF episode.
- Time curves of the UPDRS response at 10, 20, 30 and 60 minutes will be evaluated descriptively

- Change from pre-dose in UPDRS Part 3 motor score at 10 to 60 minutes following treatment of patients experiencing an OFF episode.
- Proportion of patients with a ≥ 3 , ≥ 6 , and ≥ 11 -point reduction in the UPDRS Part 3 motor score from pre-dose to post-dose, at 10 to 60 minutes.
- Proportion of patients achieving resolution of an OFF to an ON state within 60 minutes after study drug is administered in the clinic, maintaining the ON state at 60 minutes after study drug administration (per the examiner's subjective assessment).
- Patient-reported total daily OFF time, total daily ON time without dyskinesia, total daily ON time with non-troublesome dyskinesia, and total daily ON time with troublesome dyskinesia, assessed by the patient and recorded in the patient diary.
- Change from baseline visit in the 39-Item Parkinson's Disease Questionnaire (PDQ-39).

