7. INVESTIGATIONAL PLAN

This study is a 12-month, open-label, randomized, multicenter study which will evaluate the safety and effects of CVT-301 for the treatment of up to 5 OFF episodes per day in PD patients experiencing motor fluctuations (OFF episodes) and will include a concurrent observational cohort of PD patients managed using the usual standards of care. Patients must be CVT-301-naïve, however, any patients that were enrolled from the CVT-301-002 and CVT-301-003 studies under the previous version of this protocol will be allowed to continue in the study. Patients will be randomized in a 2:1 ratio to the CVT-301 treatment group (CVT-301 at a target nominal respirable dose of 50 mg LD FPD) or the observational cohort. Randomization will be differentiated by the patient's Hoehn and Yahr stage (<2.5 versus ≥ 2.5) to balance the severity of disease across each group and by screening spirometry (FEV1 $<60\%$ of predicted *or* FEV1/FVC ratio $<70\%$ versus FEV1 $\geq 60\%$ of predicted *and* FEV1/FVC ratio $\geq 70\%$).

Patients assigned to the CVT-301 treatment group may use the prescribed dose of CVT-301 as needed for the treatment of up to 5 OFF episodes per day in addition to their standard PD medications which may be modified as needed for symptomatic treatment over the 12-month study. Each treated episode will require 2-capsule inhalations (i.e., 2 capsules used in the inhaler per treated episode) to deliver the dose.

Patients assigned to the observational cohort will not receive CVT-301 but will be permitted to be managed using their standard PD medications and other PD treatment modalities, which may be modified as needed for symptomatic treatment in accordance with usual practice over the 12-month study.

For both the CVT-301 treatment group and the observational cohort, additions to and/or modification of the patient's usual PD treatment regimen may include any PD treatments that are currently approved in the patient's region. However, oral PRN LD formulations are not permitted for CVT-301-treated subjects (refer to [Section 9.4.2](#) for a list of prohibited treatments and prohibited medications). For CVT-301-treated patients, the total daily LD dose of the modified PD treatment regimen (not including CVT-301) must not exceed 1600 mg per day.

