8. STUDY POPULATION

All patients must meet the inclusion criteria and must not meet any of the exclusion criteria to be eligible for this study. Patients previously enrolled in the CVT-301-002 and CVT-301-003 studies must have completed all of the CVT-301 study visits without any safety issues that would preclude participation in this study according to the investigator. Patients who withdrew from either of the CVT-301 studies prior to completion, *for any reason*, will not be eligible.

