9.2. Randomization and Administration of Study Treatment

9.2.1. Randomization and Assignment of Study Treatment

Following completion of SV2 and prior to randomization, the patients' eligibility criteria will be reviewed by delegated staff. Upon confirmation of eligibility, the site will randomize an eligible patient using the Interactive Web Response System (IWRS). Sites must allow 7 business days between time of randomization and the first treatment visit (TV1) to allow time for drug to be shipped and received.

Eligible patients will be randomized in a 2:1 ratio to CVT-301 treatment (CVT-301 50 mg PD FPD) or the observational cohort. Randomization will be differentiated by the patient's Hoehn and Yahr stage (<2.5 versus ≥2.5) to balance the severity of disease across each treatment group and by screening spirometry (FEV1 <60% of predicted or FEV1/FVC ratio <70% versus FEV1 ≥60% of predicted and FEV1/FVC ratio ≥70%). Patients who previously completed the CVT-301-002 and CVT-301-003 studies will be assigned only to the CVT-301 treatment group. The study is an open-label study, so patients and clinical staff will not be blinded to study group assignment.

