12.3. Definition of Baseline

In all statistical analyses of the CVT-301 treatment group, the visit at which the CVT-301 treatment was initiated will be used as the baseline. However, for all patients who were included in the CVT-301-002 or CVT-301-003 studies, TV/OV1 of the CVT-301-005 study will be used as baseline. For the observational cohort, the assessments at TV/OV1 will be used as baseline.

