12.5. Safety Analysis

The disposition of the patients will be summarized by tabulating the number of screened, randomized, completed, and discontinued patients. The reasons for premature discontinuations will be tabulated.

The extent of exposure to study treatment will be summarized for the patients who received CVT-301 treatment. The time period between TV/OV1 and TV/OV6 (or Early Withdrawal Visit) will be used as the measure of extent of exposure for the patients randomized to the observational cohort. Adverse events will be tabulated by treatment group according to the Medical Dictionary for Regulatory Activities (MedDRA). Study-emergent and treatment-emergent adverse events (TEAEs) will be summarized by body system and preferred term. For patients in the observational cohort, the AEs collected between TV/OV1 and TV/OV6 (or Early Withdrawal Visit) will be considered as TEAEs. Furthermore, the time of onset of the TEAEs will be summarized.

For vital signs, ECG parameters, spirometry measurements, and DLco, the changes from pre-dose to post-dose assessments of the corresponding day will be calculated and described using descriptive statistics. For spirometry, DLco, and safety laboratory variables, the differences in pre-dose values between the study days will be described. Furthermore, the changes in the spirometry values and difference between the groups will be estimated using a Mixed Model for Repeated Measurements (MMRM) similar to the one used for the efficacy variables. The proportion of patients with abnormal spirometry values will be tabulated using different criteria for the threshold (e.g., at least 10% or 20% change from baseline at any single visit, at least 10% or 20% change from baseline on at least 2 consecutive visits). The proportions of patients meeting ATS quality criteria (and also for those 'rejected') will be summarized. All spirometry analyses will be performed both for all patients regardless of the ATS quality criteria and separately excluding the assessments not meeting the ATS quality criteria.

At least the following variables will be analyzed:

- Vital signs: standard and orthostatic systolic and diastolic BP and HR.
- ECG: HR, PR, QRS, QT and RR intervals, QTcB (Bazett's correction formula calculated as $QT/RR^{1/2}$) and QTcF (Fridericia's correction formula calculated as

QT/RR^{1/3}). ECG parameter values or parameter changes of potential clinical concern will be tabulated.

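### The CVT-301 versus observational spirometry difference includes non-randomised rollover patients in one arm, so it is not a randomised comparison and may be attenuated

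*Protocol*

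**What the plan says.** The protocol admits a closed group of rollover patients. Section 7 says that "any patients that were enrolled from the CVT-301-002 and CVT-301-003 studies under the previous version of this protocol will be allowed to continue", while exclusion criterion 15 bars anyone else with prior exposure.

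- **Allocation (Section 9.2.1):** "Patients who previously completed the CVT-301-002 and CVT-301-003 studies will be assigned only to the CVT-301 treatment group".
- **Selection (Section 8):** rollovers "must have completed all of the CVT-301 study visits without any safety issues that would preclude participation in this study", and anyone who left the earlier studies early is ineligible.
- **Baseline (Section 12.3):** the general rule is the visit at which CVT-301 was started. The exception reads: "However, for all patients who were included in the CVT-301-002 or CVT-301-003 studies, TV/OV1 of the CVT-301-005 study will be used as baseline".
- **Analysis set (Section 12.2):** "All patients who are enrolled in CVT-301-005 and receive at least 1 dose of CVT-301 will be included in the safety population".
- **Comparison (Section 12.5):** "the changes in the spirometry values and difference between the groups will be estimated using a Mixed Model for Repeated Measurements (MMRM"), using a model similar to the efficacy one. The model in Section 12.6 has visit, the stratification factors and baseline, with no term for prior study participation.

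The comparison serves a secondary objective in Section 6: "To estimate the difference between the CVT-301-patients and the observational cohort on measures of pulmonary safety". Section 5.2 gives the reason for the control: "The use of a randomized observational cohort in this study is to permit long-term contemporaneous temporal comparison to CVT-301-treated patients". Section 12.4 separates naive from rollover patients, but only for demographics and baseline characteristics.

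**The concern.** Rollovers can appear in only one of the two arms, and they passed a filter that the controls did not. Adjusting for the stratification factors and baseline does not restore randomisation.

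Two mechanisms could pull the estimate toward no harm. If a rollover had already received CVT-301 and lost FEV1 early, that loss sits inside the TV/OV1 baseline and no longer counts as change. If patients who tolerated inhalation poorly left the earlier studies, those who remain will tend to show less decline.

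This is the trial's only concurrent controlled view of lung function, and Section 12.1 expresses the study's power in terms of it. A bias that could hide harm matters in a safety study, even though no margin or test is declared and no pass/fail decision depends on it.

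**Working it through.** **Inputs.** Section 12.1 gives 250 and 115 enrolled, 25% drop-out, 188 and 86 completers, and an upper 95% limit below 0.121 L with 90% power at a true difference of zero. Section 9.2.1 gives 2:1 allocation. The protocol does not give the SD of FEV1 change, the number of rollovers or their prior exposure.

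**1. The plan's own figures.** 250 × 0.75 = 187.5 and 115 × 0.75 = 86.25, which agree with 188 and 86. The 0.121 L bound cannot be reproduced independently without an SD, so I solved for it:

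- bound = (1.960 + 1.282) × SD × √(1/188 + 1/86), with √(1/188 + 1/86) = 0.1302
- SD = 0.121 / (3.242 × 0.1302) = 0.287 L
- SE = 0.287 × 0.1302 = 0.0373 L

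A noncentral-t solution gives SD 0.2857 L and SE 0.0372 L. Both read the limit as that of a two-sided 95% interval.

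**2. Assumed rollover counts.**

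- 7: splitting 365 patients 2:1 gives 365 × 2/3 = 243.3, about 7 below 250.
- 20: 250 − 2 × 115.
- 50: a larger value, chosen only to show the range.

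Nothing in the protocol ties the excess over 2:1 to rollovers.

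**3. Shift in the estimate.** Suppose randomised CVT-301 patients truly lose 0.10 L relative to control (an assumption), and rollovers lose nothing further after TV/OV1. The pooled estimate is then smaller by 0.10 × (rollovers / 250). If rollovers keep half the decline, the shift halves. This assumes the same drop-out in rollovers and randomised patients.

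**4. Cost of a randomised-only set.** CVT-301 completers = 0.75 × (250 − rollovers), with 86 controls and the same SD.

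| Assumed rollovers | Largest shift (L) | Shift / 0.0372 | Shift if half the decline is kept (L) | Completers, CVT-301 / control | Bound at 90% power (L) |
|---|---|---|---|---|---|
| 7 | 0.0028 | 0.08 | 0.0014 | 182 / 86 | 0.122 |
| 20 | 0.0080 | 0.22 | 0.0040 | 172 / 86 | 0.123 |
| 50 | 0.0200 | 0.54 | 0.0100 | 150 / 86 | 0.126 |

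Relative to 0.121 L, the bound widens by about 0.5%, 1.5% and 4%.

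**5. Direction.** A decline that continues at a constant rate shows equally after a later baseline, so the shift is about zero. Harm that grows with cumulative exposure would make rollovers look worse and move the estimate the other way. Early, persistent loss and selection of tolerant patients both attenuate it.

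**The case against.** The strongest reply is that the SAP may settle this. Section 12 lets the SAP supersede the protocol, and Section 12.6 promises sensitivity analyses that include the definition of the analysis population. The synopsis also treats the naive-plus-rollover pool as a separate look, so the sponsor was aware of the distinction. However, those two provisions concern the exploratory endpoints. For safety the protocol states the set, the baseline exception and the between-group estimate, so this is a rule already written and not a detail left open.

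Section 5.2 itself says that rollovers continue, and both it and the objective in Section 6 refer to CVT-301 patients generally. That stands: nothing is concealed, and the wording is not contradictory. Disclosure does not make the pooled contrast randomised, though.

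The baseline choice can be defended. TV/OV1 is also the control group's baseline and gives both arms the same 12-month window, whereas an earlier-study baseline would give unequal periods. I accept this and propose no change to it.

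Finally, the counts and the 0.10 L loss are assumptions, the shift is small at 7 or 20 rollovers, the direction is not certain, and the objective is secondary. All of that stands and limits the weight of the point.

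**Conclusion.** The concern holds. As written, the between-group spirometry estimate includes patients who were never randomised, sit in one arm only and were selected for having completed an earlier study, so it is not the randomised comparison that the control cohort was set up to support.

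Attenuation is possible but not established. On the assumptions above it ranges from about zero to 0.020 L, or up to roughly half a standard error, and the upper end depends on 50 rollovers, a count with no source in the protocol. The effect falls on the interpretation of a secondary estimate. The primary objective, which is within CVT-301-treated patients, does not rest on this comparison. I would fix it because the remedy is cheap and removes the non-randomised component from the main estimate.

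**What to change.** - **Sections 12.2 and 12.5:** make randomised, CVT-301-naive patients the main set for the CVT-301 versus observational difference in FEV1, FVC and FEV1/FVC. Report the all-dosed set as a sensitivity analysis.
- **Section 12.5:** show rollover spirometry separately within the CVT-301 arm, using the split already in Section 12.4.
- **Safety population:** keep every dosed patient for adverse event tables, with a naive/rollover split.
- **Section 12.1:** give the actual rollover count and restate the bound for the expected number of randomised completers.

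The change is to wording in the protocol and SAP only, with no effect on visits, procedures or treatment. The price is the small loss of precision shown in step 4 of the working.
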